Based on our sample size calculation, a minimum of 16 hospitals with pre- and post-intervention measures is required to detect a 30-percentage point increase in the proportion of indicated SPC charts from 10% to 40% between control and intervention measures. The sample size was calculated with an alpha of 0.05 and a power of 0.80. Due to the study design (measurements taken of the outcome in a baseline period), adjustment for the correlation between pre- and post-intervention measures were made, estimated at $r=0.90$.³¹ The primary analysis will be conducted based on intention-to-treat. While only 16 hospitals are required, we have planned to include 20 on an ‘insurance principle’ in case some hospitals drop out.

Selection and randomization of hospitals

At the present time, SPC training cannot be mandated. The hospitals that take part will ultimately depend on their willingness and availability to experience training. The five-step selection and randomization process for hospitals is presented in Figure 3. **Step 1** involves obtaining contact information for all the hospitals identified as relying on R-A-G charts or two-point comparisons to present quality and safety performance metrics in their board papers (75 at the time the protocol is being written). **Step 2** involves the Making Data Count team inviting the hospitals to take up training over a specified 12-month period. As part of their informed consent, hospitals will be made aware that they may be offered training over either the initial 6-months or the later 6-months in a randomized fashion. **Step 3** involves selecting the 20 hospitals that first express an interest in taking up the training or a smaller number which do so after 30 days have passed (note that recruitment will continue until 20 express an interest – see Step 5). The Making Data Count team will email the list of

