Figure 5. Selected board papers retrieved from each hospital during the pre-intervention intervention and post intervention observation periods

Notes: The top box depicts the trusts that will experience the intervention (the intervention group), and the bottom box depicts trusts that will be placed on a waiting list to experience the intervention later (the control group). The black cells show the month of the training intervention. Green cells represent the month from which the pre-intervention papers will be retrieved, and the red cells represent the month from which the post-intervention papers will be retrieved.

For hospitals in the waitlist control group, we will form a matched list based on the order in which each is scheduled to receive training (earliest month) under the waitlist design. For example, the hospital in the intervention group scheduled to receive training first will be matched with the hospital in the waitlist group scheduled to receive training first, see the bottom half of Figure 5. This ordering is planned to minimize the possibility for waitlist hospitals to experience the training in the timespan planned for the current evaluation the waitlist control group's "post-observation" board papers will be selected from a month before each waitlist control hospital experiences training.

Outcome measures²

² The outcome measures were informed by the previous non-randomized studies discussed in the problem section and through conversations with trainers who designed the Making Data Count intervention.

Our data will be made publicly available for replication and further analyses. The main outcome measure will be the proportion of SPC charts indicated about quality and safety measures (the numerator) out of all quality and safety charts indicated in the board papers (the denominator). SPC icons will be added to the numerator and the denominator where they indicate that a unique control chart has been used but not included in the paper. Additional secondary outcome measures will be extracted from the board papers and feedback forms, as described below.

Data extraction from board papers

Quantitative measures for data contained in the board papers will be created by coding information within each board paper. Four independent reviewers (R1, R2, R3, R4) will conduct the coding over three steps.

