the board papers (the denominator), for pre-intervention and post-intervention periods. To determine the absolute effect of the intervention we will compare the proportions of charts presented as SPC charts (between intervention and control arms) for each hospital and adjust for the proportion of SPC charts in the pre-intervention period. These differences will be compared between waitlist and intervention hospitals using a t-test and reported with 95% confidence intervals (a log transformation will be used if appropriate). To determine the relative effect (risk ratio) of the intervention, we will fit a zero-inflated negative Binomial regression model (outcome data are likely to be over-dispersed with a high number of zero counts), with the outcome of the number of SPC in the post-intervention period, fixed categorical effects for the intervention and the proportion of charts which were SPC charts in the pre-intervention period, and an exposure of the number of charts (in the post-intervention period). The offset here acts much like a denominator representing the number of opportunities each chart could have been depicted in an SPC format.

A sensitivity analysis based on the per-protocol group allocations will be performed if necessary. The remaining outcomes will be reported using descriptive statistics, e.g., counts, percentages, medians, and interquartile ranges. We will describe the proportion of control charts displayed as icons versus the full control chart.

Analysis of data from feedback forms.

Likert scale responses to each question on the feedback form will be described using medians and interquartile ranges. For the free-text responses, the number of positive, negative, and neutral comments will be reported. In addition, the available free-text responses will be thematically analyzed according to Braun and Clarke's method to reveal ways to improve future training or reasons others may (or may not) want to take it up.³⁴

Ethical considerations

This research has received ethical approval to conduct from the University of Warwick Biomedical and Scientific Research Ethics committee (BSREC 100/20-21). The research team declares no conflicts of interest to disclose. The research team will work closely with NHS Improvement's Making Data Count team to design and conduct the study, and their support will be acknowledged in the final manuscript. NHS Improvement will have no role in the analysis, interpretation of data, or in writing the manuscript.

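### The count-model coefficient that the plan calls a risk ratio need not equal the ratio of SPC proportions, and can lie well below or above it

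*Combined protocol and SAP*

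**What the plan says.** Under Outcome measures, the main outcome is the number of SPC charts on quality and safety measures "out of all quality and safety charts indicated in the board papers (the denominator"). Icons that stand for a unique SPC chart are added to both numerator and denominator, so the numerator is always part of the denominator.

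Under Planned Analyses (Analysis of data from board papers), two effects are estimated. The absolute effect comes from a t-test on hospital proportions with adjustment for baseline. The relative effect, labelled a risk ratio, comes from a zero-inflated negative binomial regression of the post-intervention SPC count. Its terms are arm and the pre-intervention SPC proportion, "and an exposure of the number of charts (in the post-intervention period"). The exposure is explained thus: "The offset here acts much like a denominator representing the number of opportunities each chart could have been depicted in an SPC format". Over-dispersion and many zero counts are the stated reasons for this model.

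The plan does not say which covariates enter the zero-inflation part. Its wording also leaves unclear whether the baseline proportion enters as a category or as a continuous term.

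The design effect, under Sample size calculation, is a "30-percentage point increase in the proportion of indicated SPC charts from 10% to 40% between control and intervention measures". That implies a ratio of 40/10 = 4.0, a figure the protocol does not itself state.

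**The concern.** A reader will take the reported figure as the SPC proportion with training divided by the proportion without it. Two features of the model separate the coefficient from that quantity.

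- **One common ratio.** With baseline share as a covariate on the log scale, training is assumed to multiply every hospital's expected share by the same factor. Shares stop at 100%, so at the design effect this cannot hold for hospitals with substantial use already.
- **The zero-inflation part.** The count coefficient describes only hospitals that are not excess zeros. If training moves hospitals from no SPC charts to some, that gain can fall largely outside the coefficient.

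The ratio will be reported beside the absolute difference, and the Summary section plans a comparison with an earlier non-randomized evaluation. A ratio that conflicts with the difference next to it (30 points up from 10% is a ratio of 4) would mislead on both counts.

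**Working it through.** **1. The plan's own figure.** Inputs from Sample size calculation: 10% versus 40%, alpha 0.05 (taken as two-sided), power 0.80, r = 0.90. Per arm:

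n = [1.96 × √(2 × 0.25 × 0.75) + 0.842 × √(0.10 × 0.90 + 0.40 × 0.60)]² / 0.30² = 31.5, so 32, or 38 with continuity correction.

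The baseline adjustment multiplies by 1 − 0.90² = 0.19. Then 38 × 0.19 = 7.22, so 8 per arm and 16 in total, which reproduces "a minimum of 16 hospitals with pre- and post-intervention measures is required". Without continuity correction, 32 × 0.19 = 6.08 gives 7 per arm and 14 in total. This calculation does not involve the count model.

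**2. Can one ratio hold at every baseline share?** A ratio of 4 reaches the ceiling at 100% / 4 = 25%. Any hospital expected above 25% without training would be fitted above 100%. Two simple ways of moving the mean from 10% to 40% are a flat gain of 30 points, or conversion of one third of the remaining charts (30/90). The baseline shares below are illustrative.

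| Share without training | +30 points | Ratio | One third of gap closed | Ratio |
|---|---|---|---|---|
| 5% | 35% | 7.0 | 36.7% | 7.3 |
| 10% | 40% | 4.0 | 40% | 4.0 |
| 25% | 55% | 2.2 | 50% | 2.0 |
| 40% | 70% | 1.75 | 60% | 1.5 |

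Neither gives a common ratio, so the fitted value depends on how the model weights hospitals.

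**3. What the zero-inflation part does.** The model's mean share is (1 − π) × exp(β₀ + β₁ × arm + β₂ × baseline), where π is the excess-zero probability. The overall ratio is therefore [(1 − π₁)/(1 − π₀)] × exp(β₁), and exp(β₁) alone is not the risk ratio when training changes π.

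Take a mean of 10% with a fraction z of hospitals at zero and a flat gain of 30 points:

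- z = 30%: users average 10/0.7 = 14.3%, moving to 44.3%. Ratio among users 44.3/14.3 = 3.1.
- z = 60%: users average 10/0.4 = 25%, moving to 55%. Ratio among users 55/25 = 2.2.

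The true ratio of proportions is 40/10 = 4.0 in both cases.

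**4. Large-sample fits of the planned model.** Assumptions not in the documents: 15 to 60 charts per paper, control mean about 10%, trained mean about 40%, and 0, 30% or 60% of hospitals with no SPC charts at baseline. With 8,000 hospitals:

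- Flat +30 points, many hospitals at zero: 3.1 and 2.2, in line with step 3.
- Training converts a variable share of the remaining charts: 4.5, 5.3 and 9.0.
- Fractional logistic model averaged over hospitals: 3.9 to 4.1 throughout.

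**5. Fits with 10 + 10 hospitals** (150 simulated trials per scenario, about 30 charts per paper, linear baseline, constant zero-inflation). Medians for a true ratio of about 4:

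- Flat +30 points: 4.1 with no structural zeros, 3.9 with 30%.
- Constant ratio: 3.9. No pre-post correlation: 3.7.
- Variable share converted: 5.4, 5.6, 5.6 and 9.9 with 0, 30, 50 and 70% zeros.
- Averaged logistic model: 3.9 to 4.4.

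**6. Is the exposure the cause?** A plain negative binomial with the same exposure but no baseline term gave 3.9 to 4.1 in the large-sample fits. Replacing capped by uncapped counts with the same means moved the 20-hospital medians from 5.6 to 6.2, from 3.9 to 4.0, and left 3.9 at 3.9. The error therefore comes from the baseline term and the zero-inflation part, not from the exposure.

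**The case against.** Two stronger readings are tempting. The first is that the ratio is biased because SPC charts cannot exceed the total used as exposure. Step 6 rules this out as the direct cause: uncapping the counts removes none of the error, and the same exposure without a baseline term recovers about 4. The ceiling matters only indirectly, by making one common ratio untenable at the design effect.

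The second is that the ratio will mostly be exaggerated, with a true 4 typically estimated as 5 to 10. The documents do not support that. Such figures come mainly from a negative binomial without zero-inflation, which is not the planned model. In the 20-hospital fits of the planned model, 16% to 45% of single estimates fell between 5 and 10, never a majority, and in some large-sample settings the coefficient was too low.

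It can also be said that the eligible hospitals' papers were found to lack SPC charts, so few may exceed 25% at baseline. That limits the ceiling argument. However, the plan itself assumes a 10% level and expects many zeros, and together these imply a minority of hospitals with appreciable use (step 3).

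Finally, the Abstract defines the primary analysis as the difference in use, so the risk ratio is a companion estimate. That stands, and limits the consequence.

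**Conclusion.** The concern holds in this form: the planned coefficient is labelled a risk ratio but need not estimate the ratio of SPC proportions, even with very many hospitals. Under the assumptions in step 4, a true ratio of about 4 gave values from about 2 to 9. It was too low when training adds 30 points everywhere and many hospitals start at zero. It was too high when training converts a variable share of the remaining charts. It was close to 4 when structural zeros are few and the gain is flat or proportional; in the variable-conversion scenario without structural zeros it was still 4.5 in large samples and 5.4 in the 20-hospital runs.

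Neither the direction nor the size can be fixed from the documents, which give no chart counts, baseline distribution or form of effect. The 20-hospital estimates also vary widely between trials. The primary t-test on the absolute difference and the sample size of 16 are unaffected. The plan should be changed on this point, but the trial's main conclusion does not depend on it.

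**What to change.** Replace the count model for the relative effect with a fractional (quasi-binomial) logistic regression of each hospital's post-intervention SPC proportion on arm and the pre-intervention proportion, entered as a continuous term. From the fit, predict every hospital's proportion under training and under waitlist, average each set over all hospitals, and report the ratio of the two averages as the risk ratio. Take the 95% interval from a leave-one-hospital-out jackknife with a t reference. The same fit gives a matching risk difference.

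In simulations with 20 hospitals and 30% or 60% of them at zero (400 trials per scenario), this interval covered the true ratio in 95% to 98% of trials. The comparator in those runs was a plain negative binomial (63% to 87%), so they do not measure coverage for the planned zero-inflated model.

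The cost is a change of wording and a few lines of code, with no new data. There are two small drawbacks. The ratio is no longer a single model coefficient, and it is undefined if no control hospital shows an SPC chart, as any ratio would be.

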¹ The intervention will be described more briefly within the final manuscript and more fully in an appendix according to the TiDIER framework.¹

tailored for two sets of attendees: board members and data analysts. Board member and analyst training sessions are delivered as close as possible in time, typically within the same month. Training sessions for board members are usually delivered over about one-and-a-half hours and focus more heavily on the benefits of control charts compared to other charts. Training sessions for analysts are usually delivered over three hours and focus more heavily on the structure and interpretation of the individual and moving range charts (X-mR charts).

The training sessions are delivered by one of two trainers with academic accreditation and work experience in data analytics. The training was originally delivered face-to-face at the hospitals, but since the COVID-19 pandemic has been adapted to an online environment and can now be offered in either format. The training sessions are tailored for each hospital, by creating, presenting, and discussing charts constructed from that hospital's recent data. Anonymized examples of the slides used during the training during this study will be provided as appendixes in the final manuscript. Guidebooks supplementing the training are available online.²⁶ Any modifications made to the training regime and any unexpected events that interfere with their planned delivery will be reported in the final manuscript.

During training sessions, trainees explore the strengths and weaknesses of different presentation methods. SPC charts are discussed in-depth to explain what they are, how to construct them, and why they are recommended. Data analysts are told how to prepare control charts to present in their board papers and to place the control limits at three-sigma. If analysts deviate from the 3-sigma rule they are asked to explain how and why in supporting text in a box near the control chart. The supporting text might also include explanations for performance variations and recommendations for improvements, see Figure 1.

Figure 1. Example provided for how supporting text should accompany charts.

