Step 1: R1 will download the papers. From each paper, R1 and R2 will independently extract the following three types of items: (A) the charts that appear, (B) SPC icons that appear indicating a control chart has been used, and (C) any supporting text aside charts that appear as instructed by the Making Data Count training, see Figure 1. They will then independently code aspects of the extracted charts and icons as described in Table 3.

Table 3. Step 1 coded elements.

Extracted item to be coded	Code Name	Explanation													
Charts	Quality and Safety-Chart	whether the chart is about a quality or safety measure (yes/no)													
SPC Icons	Quality and Safety-Icon	whether the icon is about a quality or safety measure (yes/no)													
→ If “yes” to Quality and Safety-Icon, then the following element also coded															
Quality and Safety SPC Icons	Icon indicating unique SPC chart	whether the SPC icons indicates a unique chart (yes/no) – a “yes” response indicates that this icon is added to the total numbers of control charts (numerator) and charts (denominator)													
Quality and Safety SPC Icons	Icon – Purpose	whether the SPC icon is being presented for “assurance” purposes or to convey information about process “variation” 
  
 Variation	Assurance	
   
 							
  
	Variation			Assurance									
Variation			Assurance												

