Step 2: R1 will take a screenshot of each quality and safety chart and the supporting text, removing identifying features, e.g., the name of the hospital and/or calendar dates, and send the redacted charts to R3 and R4. A screen shot of the supporting text will be taken, also removing identifying features.

Step 3: R3 and R4 will independently code features of the charts and supporting texts, which are described in Table 4.

Table 4. Step 4 coded elements

Extracted item to be coded	Code Name	Explanation
Quality and Safety Charts	Chart type	whether the chart is a time series chart, between subjects chart, time and between chart, or other (e.g., pie). The categories will be exclusive, such that only one may be selected.
Quality and Safety Charts	SPC?	whether the chart is a SPC chart (yes/no)
→If “yes” to SPC? then the following elements are also coded		
Quality and Safety Charts SPC Charts	Recalculations	whether the control limits are recalculated (yes/no)
Quality and Safety Charts SPC Charts	Special Cause Highlights	whether any data are highlighted as special cause (yes/no)
	...Special Cause Highlights-as recommended	and if “yes” whether the recommended blue/orange colors are used (yes/no)
Quality and Safety Charts SPC Charts	R-A-G ³	whether any data are highlighted as R-A-G colors (yes/no)
	...R-A-G as NOT recommended	and if “yes” whether those R-A-G colors follow the former performance-based target model of data monitoring (yes/no)
Quality and Safety Charts SPC Charts	Labels	whether there are labels on the chart describing where process labels are set (yes/no)
	...Labels	and if “yes” AND are the labels different from “3-sigma” (yes/no)
Supporting text	Explaining where control lines are set	whether the text explains where the control lines are set (yes/no)
Supporting text	Reasons for variations	whether the text posits reasons for variation (yes/no)
Supporting text	Suggestions for improvements	whether the text suggests interventions (yes/no)

³ Making Data Count trainers believe it is valuable to extract data about whether RAG colorings continue to be used for at least two reasons. First, RAG colors are predominantly used by the trust being invited to attend the training. Second, the training intervention explicitly informs attenders that RAG presentations are not well suited to quality improvement methodologies and urges attenders to move away from RAG presentations towards SPC presentations.

Blinding and agreement

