Initially, codes will be independently assigned. Disagreements will be resolved through consensus discussions. Any disagreements that cannot be resolved will be referred to the chief investigator. It is not possible to blind reviewers R1 and R2 to the board papers group or time-period, as they are extracting charts from the published board papers. R3 and R4 will be blinded and will be instructed to inform R1 if they are unblinded to experimental group at any point, and whether/how often they are unblinded will be reported in the final manuscript.

Data extraction from feedback forms

Data extracted from feedback forms will include trainees' Likert ratings and free-text responses, see Table 2. These data will be compiled into an Excel file. R1 and R2 will independently code whether each free-text response is positive (e.g., "The training was practically useful."), negative (e.g., "The training went so fast that I couldn't keep up."), or neutral (e.g., "Handouts provided.").

Planned Analyses*Analysis of data from board papers*

The hospitals will be described according to how many days it took them to accept the training invitation, along with their size (number of beds), and local deprivation status, as indicated on NHS Digital's Peer Finder Tool.³³ The inter-rater reliability of the data extracted from the board papers will be calculated using Kappa statistics and percentage agreement to quantify the level of agreement between reviewers. Descriptive statistics will enumerate the proportion of control charts that show the full detail and those appearing as icons.

The main analysis will examine the effect of the training intervention. For each hospital, we will observe the proportion of indicated SPC charts, including SPC icons, about quality and safety measures (the numerator) out of all quality and safety charts indicated in

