DISCUSSION

Summary

The summary will highlight whether the Making Data Count training intervention significantly increased control charts usage. Then it will compare the present results with those found in the previous, non-randomized evaluation.³⁵ We will explore how the responses to the feedback forms help us understand the effectiveness of the training. The literature will be reviewed for more recent publications nearer to the time this manuscript is written. Implications for clinical practice across types of care (e.g., health and social care) will be considered, along with the potential for the intervention's effectiveness to generalize to organizations outside England.

Limitations

Limitations are acknowledged within this protocol having to do with methods and the potential for our results to generalize. Regarding study methods, we are unable to blind the first set of reviewers to whether a hospital belongs to the intervention or control group. This is not possible because they will be looking directly at the board papers as they extract the initial information, and the board papers will inevitably contain identifiable information. The second set of reviewers will be blinded, as they will only be looking at extracted charts. Second, while board papers provide an objective measure of whether control charts are used, they are silent on how control charts are used. While the existence of control charts is a

necessary pre-condition for their being used well, it is possible that they are not being used as part of a broader quality improvement methodology that could positively impact patient care.

In that sense, our study only seeks to establish whether the necessary conditions for SPC-based improvement have been met. A future study may investigate how SPCs are used.

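### The blind for R3 and R4 is said to rest on their seeing only charts, but they also code the training-style supporting text, and nothing requires 'SPC?' to be coded first

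*Combined protocol and SAP*

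**What the plan says.** Four parts of the combined protocol and SAP bear on this.

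- **Discussion, Limitations.** The first pair of reviewers cannot be blinded. Of the second pair it says: "The second set of reviewers will be blinded, as they will only be looking at extracted charts".
- **Data extraction from board papers, Step 1.** Besides charts and icons, R1 and R2 extract "any supporting text aside charts that appear as instructed by the Making Data Count training".
- **Steps 2 and 3, with Table 4.** "R1 will take a screenshot of each quality and safety chart and the supporting text, removing identifying features", the examples of such features being "e.g., the name of the hospital and/or calendar dates, and send the redacted charts to R3 and R4". A separate sentence says the supporting text is also captured with identifying features removed. Then "R3 and R4 will independently code features of the charts and supporting texts, which are described in Table 4". Table 4 lists chart type, 'SPC?' and further chart features, followed by three supporting-text items: the placing of the control lines, suggested causes of variation, and proposed improvements.
- **Blinding and agreement.** R3 and R4 "will be instructed to inform R1 if they are unblinded to experimental group at any point", and the final manuscript will report whether and how often this happened. Codes are first assigned independently, disagreements go to consensus, and unresolved ones go to the chief investigator. Planned Analyses adds kappa and percentage agreement.

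**The concern.** The reason given for the blind is not what the extraction steps deliver. The coders handle a second kind of material, and it is selected for its resemblance to what the training teaches. The Intervention section describes supporting text as training content: if analysts depart from three-sigma limits, "they are asked to explain how and why in supporting text in a box near the control chart", and the text may also carry explanations and recommendations.

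This matters because of 'SPC?'. Under Outcome measures, the primary outcome is the share of quality and safety charts that are SPC charts, with unique icons added to numerator and denominator. The icon codes and the quality-and-safety codes come from R1 and R2, whom the plan declares unblinded. 'SPC?' on displayed charts is therefore the one numerator code that the plan protects by blinding. If the text suggests trained status before that code is fixed, an unclear chart could be read more generously in a trained hospital's paper.

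**Working it through.** The documents give no figure for this point, so no arithmetic on bias applies. The check sets the sections side by side.

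1. **Do R3 and R4 see the text?** The transfer sentence in Step 2 names only the redacted charts. Step 3, however, says "R3 and R4 will independently code features of the charts and supporting texts", and Table 4 gives them three text items. They cannot code text they have not received. The Limitations sentence is therefore inaccurate, whatever the size of any bias.

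2. **Can the text hint at training?** Step 1 defines the extracted text by reference to the training, and the Intervention section describes it as training content. A hint is therefore plausible, though not certain.

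3. **What would a hint reveal?** Under Selection of board papers from hospitals, 20 hospitals give two papers each, 20 × 2 = 40. The pre-intervention papers of both arms and the post-observation papers of the waitlist arm all precede that hospital's training. Only the 10 post-intervention papers of the intervention arm follow it, leaving 40 − 10 = 30 untrained papers. If the schedule runs as planned, recognising a trained paper identifies both arm and period.

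4. **Does it reach the primary outcome?** Yes, for displayed charts. Table 4 asks only for a yes or no on 'SPC?' and sets no criteria for unclear charts. One text item, on where the control lines lie, bears on the same judgement.

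5. **Is the order fixed?** No. Chart and text codes both belong to Step 3, and nothing requires 'SPC?' to be settled before the text is opened.

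6. **Do the safeguards close the gap?**
   - Redaction is aimed at identifying features. The examples are hospital name and calendar dates; training-specific wording is not mentioned.
   - Reporting of unblinding captures only what a coder notices and declares. It records the event and does not prevent it.
   - Independent double coding, consensus and kappa address disagreement between coders. They cannot detect a lean that both coders share from seeing the same text.

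**The case against.** The case on the other side has real force.

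- **Pairing is not stated.** A reader might infer that chart and text arrive as one package and that 'SPC?' is judged with the text in view. The plan does not say so; it is silent on pairing and order. What stands is the silence.
- **There are several safeguards.** A reader might conclude that self-report is the sole check. It is not: redaction, independent coding, consensus, referral and agreement statistics are all planned. The redaction list is open-ended, so it does not rule out removing references to the training. It does not require it either.
- **The text is a weak cue.** Explanations and recommendations are common commentary. The guidebooks are online, so untrained hospitals may write similar text. The charts themselves may hint at training through the recommended blue and orange highlights or three-sigma labels, and withholding text would not change that. This stands, and it limits what any fix can achieve.
- **Most 'SPC?' calls should be clear.** A reader might offer charts with limits other than three sigma as unclear cases. The plan does not support that: Table 4 asks about labels that differ from 3-sigma only after 'SPC?' is yes, so such charts already count as SPC.
- **The larger exposure is disclosed.** R1 and R2 are openly unblinded and decide which charts and icons count. This is true, but it is no reason to weaken the blinding that remains.

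**Conclusion.** The point holds as a contradiction between sections and an avoidable weakness in the blinding of one code that feeds the primary numerator. It is a minor point, but worth correcting.

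The size of any bias cannot be derived from the documents. It would depend on how many displayed charts are unclear, how often the text gives status away, how far that moves a coder, and what share of the denominator is icons. None of these is given. It is probably small, because 'SPC?' is a fairly objective item coded by two people, and it is zero if unclear charts are judged alike whatever the text suggests. A reader might infer an inflation of several percentage points to set against the 30-point target, or that the blind has failed. The documents support neither: any such figure would be pure assumption, and no section shows that the text does reveal status.

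The conclusion assumes only that R3 and R4 receive the text that Step 3 has them code, and that text chosen for following the training can sometimes be recognised as such.

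**What to change.** 1. Split Step 3. R3 and R4 first code chart type and 'SPC?' from redacted chart-only images, pooled over all papers in random order, and those codes are locked.
2. Then release the supporting text, redacted as now and with references to the training also removed, for its own three codes.
3. Correct the Limitations sentence to say that R3 and R4 see both charts and supporting text, and state the order of coding.

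The cost is two coding passes instead of one, with the same reviewers and the same items. A guess of trained or untrained status after the first pass is not worth adding. Taken before the text is released, it could not test whether the text unblinds, and accurate guesses might only reflect that training increased SPC use.
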